## **10.8.2.** Respiratory Examination

A respiratory examination will be required to be performed for all subjects at all scheduled visits, according to Table 1. At screening, the investigator should specifically question all subjects about any medical history of asthma and their respiratory health (eg, wheezing, allergies, and infections). After the screening visit, all subjects will be asked non-leading questions about any respiratory changes.

[figure not shown]
Results will be summarized by treatment group and visit for each question in respiratory examination form per CRF.

#### **10.8.3.** Peak Expiratory Flow (PEF)

PEF measurements will be performed for all subjects at Screening, Baseline, Week 8, Week 16, Follow-up Visit, and Early Termination Visit. For subjects reporting a medical history of asthma, PEF measurements will be performed at all visits during the clinical study (ie, PEF testing at Visit 3 and 5 will occur in asthmatic subjects only). For subjects diagnosed with de novo asthma, PEF measurements will be performed at all visits starting with the visit in which the diagnosis was confirmed.

Results from PEF testing [actual PEF rate (L/min) and/or actual PEF rate of the predicated value (%)] will be summarized by treatment group and visit using descriptive statistics, including observed values and change from baseline values.

Number and frequency of subjects with abnormal PEF (actual PEF < 80% of the predictive value) will be summarized by visit, treatment group.

Statistical Analysis Plan
Sponsor: Galderma S.A./Galderma R&D, LLC; Protocol No.: RD.06.SPR.118380 V4.0, 06Jul2022

All PK parameters will be listed by subject.

# 13. Interim Analyses

No interim analysis will be performed.

# 14. Changes from Analysis Planned in Protocol

### 14.1. Concomitant Medications and Therapies

In protocol Section 9.6 (Prior and Concomitant Therapies), concomitant medications/therapies are defined as any therapies taken during the study (ie, from the screening visit to the end of study).

However, for the analysis purpose, the medications are classified as taken prior or concomitantly with the study drug administration. Concomitant medications/therapies are defined as medications/ therapies which start or stop on or after the 1st injection of study drug. The purpose of this analysis is to provide information separately on:

- the medication taken in addition to the study drug;
- the medication taken prior to the study drug administration.

This analysis could be used to identify any medication that could potentially interact with the study drug.

### 14.2. Analysis of Secondary Endpoints

In protocol Section 16.5.1 (Secondary Efficacy Endpoints), for binary efficacy endpoints, one sensitivity analysis is to have CMH analysis conducted based on observed data, with data post rescue medication set to treatment failure. This sensitivity analysis is removed in current SAP, since the rest analyses provide sufficient assessment.

For continuous secondary efficacy endpoints, analysis using ANCOVA on OC will not be performed as the current analyses provide sufficient assessment on these endpoints.

MI analyses will be performed using MAR assumption instead of MNAR assumption. This is to align with the overall Arcadia program of the study drug; also, the MNAR models require to have sufficient amount of non-missing data in reference group in each of the stratums, and the issue of MNAR models failing to impute the missing data with MNAR assumption due to lack of sufficient non-missing data in the reference group was observed during the dry-run. Thus, it is determined that MI with MAR assumption will be employed in the final run.

### 14.3. Estimands Section

Description of estimands for main primary endpoints were listed in section 3.1

#### 14.4. Analysis of Vaccine Secondary Endpoints

Additional vaccine secondary endpoints will be provided, computing the Geometric Mean Concentration/Titers ratios from Week 16 to Baseline

## 15. Programming Considerations

#### 15.1. General Considerations

- One SAS program can create several outputs.
- One output file can contain several outputs.
- Output files will be delivered in Word format (.rtf) and portable document format (.pdf).
- Numbering of TFLs will follow International Conference on Harmonization (ICH) E3 guidance.

# 15.2. Table, Listing, and Figure Format

#### **15.2.1.** General

- All TFLs will be produced in landscape format, unless otherwise specified.
- All TFLs will be produced using the Courier New font, size 8.
- The data displays for all TFLs will have a minimum blank 1-inch margin on all 4 sides.
- Headers and footers for figures will be in Courier New font, size 8.
- Legends will be used for all figures with more than 1 variable, group, or item displayed.
- TFLs will be in black and white (no color), unless otherwise specified
- Specialized text styles, such as bolding, italics, borders, shading, and superscripted and subscripted text, will not be used in the TFLs, unless otherwise specified.
- Only standard keyboard characters will be used in the TFLs. Special characters, such as non-printable control characters, printer-specific, or font-specific characters, will not be used.
   Hexadecimal-derived characters will be used, where possible, if they are appropriate to help display math symbols (e.g., μ). Certain subscripts and superscripts (e.g., cm², Cmax) will be employed on a case-by-case basis.
- Mixed case will be used for all titles, footnotes, column headers, and programmer-supplied formats, as appropriate.

#### **15.2.2.** Headers

• All output should have the following header at the top left of each page:

Galderma Protocol RD.06.SPR.118380 Draft/Final Run

• All output should have Page n of N at the top or bottom right corner of each page. TFLs are internally paginated in relation to the total length (i.e., the page number should appear sequentially as page n of N, where N is the total number of pages in the table).

 The date output was generated should appear along with the program name as a footer on each page.

#### **15.2.3.** Display Titles

• Each output are identified by the designation and a numeral. (i.e., Table 14.1.1). The title is centered. The analysis set is identified on the line immediately following the title. The title and table designation are single-spaced. A solid line spanning the margins will separate the display titles from the column headers. There will be 1 blank line between the last title and the solid line.

Table x.y.z
First Line of Title
Second Line of Title if Needed
(XX Analysis Set)

#### 15.2.4. Column Headers

- Column headings are displayed immediately below the solid line described above in initial uppercase characters.
- Analysis set sizes will be presented for each treatment group in the column heading as (N=xx) (or
  in the row headings, if applicable). This is distinct from the 'n' used for the descriptive statistics
  representing the number of subjects in the analysis set.
- The order of treatments in the tables and listings will be Placebo first in the case of placebo controlled studies and Active comparators first in the case of active comparator trials, followed by a total column (if applicable).

### **15.2.5.** Body of the Data Display

#### **15.2.5.1.** General Conventions

Data in columns of a table or listing are formatted as follows:

- Alphanumeric values are left-justified;
- Whole numbers (e.g., counts) are right-justified;
- Numbers containing fractional portions are decimal aligned.

#### 15.2.5.2. Table Conventions

- Units will be included where available.
- If the categories of a parameter are ordered, then all categories between the maximum and minimum category are presented in the table, even if n=0 for all treatment groups in a given category that is between the minimum and maximum level for that parameter.
- If the categories are not ordered (e.g., Medical History, Reasons for Discontinuation from the Study, etc.), then only those categories for which there is at least 1 subject represented in 1 or more groups are included.

- Unless otherwise specified, the estimated mean, median, Q1 and Q3 for a set of values are printed out to 1 more significant digit than the original values, and standard deviations are printed out to 2 more significant digits than the original values. The minimum and maximum should report the same significant digits as the original values.
- P-values are output in the format: "0.xxx", where xxx is the value rounded to 3 decimal places. Every p-value less than 0.001 will be presented as <0.001. If the p-value is returned as >0.999, then present as >0.999.
- Percentage values are printed to one decimal place, in parentheses with no spaces, one space
  after the count (e.g., 7 (12.8%), 13 (5.4%)). Unless otherwise noted, for all percentages, the
  number of subjects in the analysis set for the treatment group will be the denominator. Percentages
  after zero counts should not be displayed and percentages equating to 100% are presented as
  100%, without decimal places.
- Where a category with a subheading (such as system organ class) has to be split over more than one page, output the subheading followed by "(cont)" at the top of each subsequent page. The overall summary statistics for the subheading should only be output on the first relevant page.

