#### **10.8.1.** Asthma Control Test (ACT)

Subjects with a medical history of asthma will take the ACT at all visits according to Table 1. Subjects with a new (de novo) diagnosis of asthma will take the ACT beginning at the visit the diagnosis was first confirmed and at all subsequent study visits thereafter. Subjects with an ACT score ≤ 19 will be referred to the physician managing their asthma.

The ACT is an assessment to determine if a subject's asthma symptoms are well controlled. The ACT is designed for adults and adolescents 12 years or older and is composed of 5 questions. For each question, the subject will choose the best answer out of 5 possible answers. The test provides a

numerical score ranging from 5 to 25 to assess asthma control; a higher score indicates better asthma control while a score of 19 or less indicates the subject's asthma may not be under control.

Results from ACT test will be summarized by treatment group and visit using descriptive statistics, including observed values and change from baseline values.

Number and frequency of subjects with ACT score ≤ 19 will be summarized by visit and by treatment group.

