14.3.2.5	Listing of Adjudicated Asthma Treatment-Emergent Adverse Events (TEAEs) Comments	SAF
14.3.4.1.1.1	Summary of Observed Values and Changes from Baseline for Hematology Value by Visit	SAF
14.3.4.1.1.2	Shift from Baseline of Hematology Values by Visit and by Reference Range	SAF
14.3.4.1.1.3	Proportions of Subjects with Potentially Clinically Significant Hematology Value	SAF
14.3.4.1.1.4	Listing of Subjects with Potentially Clinically Significant Hematology Value	SAF
14.3.4.1.2.1	Summary of Observed Values and Changes from Baseline for Chemistry Value by Visit	SAF
14.3.4.1.2.2	Shift from Baseline of Chemistry Values by Visit and by Reference Range	SAF
14.3.4.1.2.3	Proportions of Subjects with Potentially Clinically Significant Chemistry Value	SAF
14.3.4.1.2.4	Listing of Subjects with Potentially Clinically Significant Chemistry Value	SAF
14.3.4.1.3.1	Summary of Observed Values and Changes from Baseline for Urinalysis Value by Visit	SAF
14.3.4.1.3.2	Shift from Baseline of Urinalysis Values by Visit and by Reference Range	SAF
14.3.4.1.3.3	Proportions of Subjects with Potentially Clinically Significant Urinalysis Value	SAF
14.3.4.1.3.4	Listing of Subjects with Potentially Clinically Significant Urinalysis Value	SAF

14.3.4.2.1	Summary of Observed Values and Changes from Baseline for Vital Signs, Height and Weight by Visit	SAF
14.3.4.2.2	Shift from Baseline of Vital Signs, Height and Weight by Visit and by Reference Range	SAF
14.3.4.2.3	Proportions of Subjects with Potentially Clinically Significant Vital Signs, Height and Weight	SAF
14.3.4.2.4	Listing of Subjects with Potentially Clinically Significant Vital Signs, Height and Weight	SAF
14.3.4.3	Summary of 12-Lead Electrocardiogram (ECG) Overall Interpretation	SAF
14.3.4.4	Summary of Physical Examination	SAF
14.3.4.5.1	Summary of Asthma Control Test (ACT)	SAF
14.3.4.5.2	Summary of Asthma Control Test (ACT) Score <= 19	SAF
14.3.4.6	Summary of Respiratory Examination	SAF
14.3.4.7.1	Summary of Peak Expiratory Flow (PEF)	SAF
14.3.4.7.2	Summary of Peak Expiratory Flow (PEF) < 80% of Predicted Value	SAF

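### By default, the percentages with ACT ≤ 19, and with PEF < 80% at Visits 3 and 5, are divided by the whole safety population although only subjects with asthma are tested

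*SAP*

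**What the plan says.** **Denominator.** For every percentage without a noted exception, SAP 15.2.5.2 states that the "number of subjects in the analysis set for the treatment group will be the denominator".

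**Outputs.** SAP 10.8.1: "Number and frequency of subjects with ACT score ≤ 19 will be summarized by visit and by treatment group". SAP 10.8.3: "Number and frequency of subjects with abnormal PEF (actual PEF < 80% of the predictive value) will be summarized by visit, treatment group". Neither section names a denominator. The index in SAP 17 lists Table 14.3.4.5.2, "Summary of Asthma Control Test (ACT) Score <= 19", and the matching PEF table, 14.3.4.7.2, both on the SAF. SAP 5.2 defines the SAF as all randomized subjects with at least one administration of study drug, whatever their asthma status.

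**Who is tested.** For the ACT, SAP 10.8.1 says: "Subjects with a medical history of asthma will take the ACT at all visits according to Table 1". Subjects with de novo asthma join from the visit at which the diagnosis is confirmed; nobody else takes it. For PEF, SAP 10.8.3 says: "PEF measurements will be performed for all subjects at Screening, Baseline, Week 8, Week 16, Follow-up Visit, and Early Termination Visit". It adds that "PEF testing at Visit 3 and 5 will occur in asthmatic subjects only".

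**Who attends.** Protocol 7.1 does not require the follow-up visit of subjects who enter the long-term extension. Under Protocol 9.7.1 the early termination visit applies only to subjects who leave the study early.

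**The concern.** A subject who never took the ACT cannot score 19 or less, but under the default that subject still sits in the denominator. The table then reads as though the untested subjects had been tested and found above the threshold. The same happens with PEF at the visits where only asthmatic subjects are measured, and for subjects not seen at follow-up or early termination.

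These percentages bear on a named risk. Protocol 5.3.1 lists new or worsening asthma among the important potential risks of nemolizumab, Protocol 13.1.1 makes it an AESI, and Protocol 15.2 has an adjudication committee review it. Protocol 5.3.1 also describes ACT ≤ 19 and PEF below 80% of predicted as grounds for exclusion at entry, so values beyond these thresholds after baseline are what the two tables exist to show.

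A diluted percentage also carries the number of asthmatic subjects in each arm into the comparison. Baseline disease severity is the only stated stratification factor (Protocol 9.3.1, partly redacted), so asthma history may differ between arms by chance.

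**Working it through.** The plan states no ACT or PEF percentage, so there is no figure to reproduce. The check is first of the text, then of the arithmetic.

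**Does the default apply?**
- In SAP 7.1, frequencies means subject number and percent, so the requested frequency in 10.8.1 and 10.8.3 includes a percentage.
- Where the SAP wants another denominator it says so: site accounting in 7.1 and the observed-case analysis in 8.1.2.
- SAP 6.1 lists a number of observations, a frequency and a percentage for categorical variables, but does not make the number of observations the denominator.

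So the text of 10.8.1 and 10.8.3 leaves the rule of 15.2.5.2 in force.

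**Which visits are Visits 3 and 5?** The schedule of assessments is redacted. The list of PEF visits for all subjects leaves out Weeks 4 and 12, so these are taken to be Visits 3 and 5. This is an inference.

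**Size.** Let x be the subjects meeting the threshold, m those tested and N the SAF in the arm. Then

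printed % = x/N = (x/m) × (m/N).

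The factor m/N is exact. N = 123 per arm is taken from SAP 3.5, treating all randomized subjects as dosed. The asthma shares and event counts below are assumptions.

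| Assumed asthma share | Tested m | ACT ≤ 19, x | x/m | x/123 | m/123 |
|---|---|---|---|---|---|
| 10% | 12 | 2 | 16.7% | 1.6% | 0.10 |
| 20% | 25 | 5 | 20.0% | 4.1% | 0.20 |
| 30% | 37 | 7 | 18.9% | 5.7% | 0.30 |
| 50% | 62 | 12 | 19.4% | 9.8% | 0.50 |

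**Arm comparison.** Suppose 25 subjects have asthma in one arm and 37 in the other, with 5 and 7 at ACT ≤ 19. Among those tested the rates are 5/25 = 20.0% and 7/37 = 18.9%. Under the default they print as 5/123 = 4.1% and 7/123 = 5.7%, so the order is reversed.

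**PEF across visits.** Assume a 20% asthma share and PEF < 80% in 20% of asthmatic and 5% of other subjects.
- Weeks 8 and 16, all tested: 5 of 25 plus 5 of 98, or 10/123 = 8.1%.
- Visits 3 and 5, default denominator: 5/123 = 4.1%.
- Visits 3 and 5, those tested: 5/25 = 20.0%.

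Nothing changes clinically in this example, yet the printed figure moves between 8.1% and 4.1%. Changing the denominator alone gives 8.1% and 20.0%, which is still a shift in who is measured. Only a row for the same asthma subset at Weeks 8 and 16 (again 5/25 = 20.0%) makes the visits comparable.

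**The case against.** The strongest reply is that the rule is a layout convention that expressly allows exceptions, and that the table shells and footnotes, where an exception could be noted, are not in the documents. That stands as a limit: the outputs may turn out right. It does not remove the rule, which is stated, and which the two sections requesting the percentages do not override.

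Second, little is lost. Counts are unaffected, and the companion descriptive tables (14.3.4.5.1 and 14.3.4.7.1) carry the number tested, so a reader can recompute the percentage. The asthma signal is also reported elsewhere: AESIs in Table 14.3.1.9, adjudicated events in Tables 14.3.1.13 to 14.3.1.15, and, under SAP 10.8, a listing of subjects with a drop of at least 15% in PEF or ACT. This stands. A reader might infer that the plan hides an asthma signal; the documents do not support that.

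Third, a reader might take the percentage among those tested to be the true rate. It is not simply that. Count over SAF is a legitimate randomized comparison of how many treated subjects were found below the threshold. The tested group includes de novo cases, so it is partly formed after randomization by an event the drug might cause. If 20 are tested in one arm and 30 in the other, with 5 at ACT ≤ 19 in each, the tested-only rates are 25.0% and 16.7%. If the extra 10 were de novo cases on drug, that arm would look better because it produced more asthma. This stands, and the fix has to deal with it.

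**Conclusion.** The point holds within limits. As written, the SAP divides the ACT ≤ 19 percentages at every visit, and the PEF < 80% percentages at Visits 3 and 5, by subjects most of whom may never have been tested. The follow-up and early termination percentages include non-attenders as well.

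The dilution factor m/N is exact, but its value is unknown because the documents give no asthma share. It is about 0.1 to 0.5 over assumed shares of 10% to 50%. A reader might infer a several-fold understatement as fact; at a 50% share it is about twofold.

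Nor should the point be carried over to PEF as a whole. At Baseline and Weeks 8 and 16 PEF is planned for all subjects, so there is no structural dilution there. The ACT is a subject-completed questionnaire and should not be described as an objective measure. The primary endpoint is untouched, and no between-arm test is specified for these two tables. What remains is a safety percentage that can mislead on a named risk and is easily put right.

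**What to change.** - In SAP 10.8.1 and 10.8.3, state that the denominator is subjects with a non-missing ACT (or PEF) result at that visit, and print that n in Tables 14.3.4.5.2 and 14.3.4.7.2.
- Present subjects with a baseline history of asthma separately from de novo cases, so that the arm comparison is not conditioned on a diagnosis made after randomization.
- Label PEF at Visits 3 and 5 as asthmatic subjects only. Show Weeks 8 and 16 both overall and for subjects with a history of asthma.

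The cost is SAP wording and slightly more table programming. The displayed percentages will be higher and rest on smaller denominators, so they will be less stable. No new data are needed.

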#### **15.2.5.3.** Listing Conventions

- Listings will be sorted for presentation in order of treatment groups as above, subject number, visit/collection day, and visit/collection time.
- Missing data are represented on subject listings as either a hyphen ("-") with a corresponding footnote ("- = unknown or not evaluated"), or as "N/A", with the footnote "N/A = not applicable", whichever is appropriate.
- Dates are printed in SAS DATE9.format ("DDMMMYYYY": 01JUL2000). Missing portions of dates
  are represented on subject listings as dashes (--JUL2000). Dates that are missing because they
  are not applicable for the subject are output as "N/A", unless otherwise specified.
- All observed time values are to be presented using a 24-hour clock HH:MM or HH:MM:SS format (e.g., 11:26:45, or 11:26). Time will only be reported if it was measured as part of the study.
- Units will be included where available.

#### **15.2.6.** Footnotes

- A solid line spanning the margins will separate the body of the data display from the footnotes.
- All footnotes will be left justified with single-line spacing immediately below the solid line underneath the data display.
- Footnotes should always begin with "Note:" if an informational footnote, or 1, 2, 3, etc. if a reference footnote. Each new footnote should start on a new line, where possible.
- Subject specific footnotes are avoided, where possible.

Sponsor: Galderma S.A./Galderma R&D, LLC; Protocol No.: RD.06.SPR.118380 V4.0, 06Jul2022

- Footnotes will be used sparingly and add value to the table, figure, or listing. If more than six lines of footnotes are planned, then a cover page is strongly recommended to be used to display footnotes, and only those essential to comprehension of the data will be repeated on each page.
- The last line of the footnote section will be a standard source line that indicates the name of the program used to produce the data display, date the program was run (eg., 'Program: myprogram.sas Table Generation: DDMMMYYY HH:MM').

# 16. Quality Control

SAS programs are developed to produce output such as analysis data sets, summary tables, data listings, figures or statistical analyses.

PPD End-to-End Process of the Production of Analysis Datasets (ADs) and Tables, Figures and Listings (TFLs) SOP (3922) and the SAS Programming and Validation Plan describe the quality control procedures that are performed for all SAS programs and output. Quality control is defined here as the operational techniques and activities undertaken to verify that the SAS programs produce the output by checking for their logic, efficiency and commenting and by review of the produced output.

# 17. Index of Tables

Table Number	Name	Analysis Set
14.1.1.1	Subject Disposition	Screened
14.1.1.2	Subject Accounting by Overall and Site	Population Screened
14.1.1.3	Subject Accounting by Visit	Population ITT
14.1.2	Major and COVID19-related Protocol Deviations	ITT
14.1.3.1.1	Demographic and Baseline Characteristics	ITT
14.1.3.1.2	Demographic and Baseline Characteristics	SAF
14.1.3.1.3	Demographic and Baseline Characteristics	mITT
14.1.3.2.1	Summary of Medical History	ITT
14.1.3.2.2	Summary of Medical History	Safety
14.1.3.2.3	Summary of Medical History	mITT
14.1.3.3.1	Summary of Prior Medical and Surgical Procedure	ITT
14.1.3.3.2	Summary of Concomitant Medical and Surgical Procedure	ITT
14.1.4.1.1	Summary of Prior Medications	ITT
14.1.4.1.2	Summary of Prior Medications	Safety
14.1.4.1.3	Summary of Prior Medications	mITT
14.1.4.2.1	Summary of Concomitant Medications	ITT
14.1.4.2.2	Summary of Concomitant Medications	Safety
14.1.4.2.3	Summary of Concomitant Medications	mITT
14.1.4.3.1	Summary of Rescue Medications during Treatment Period	ITT
14.1.4.3.2	Summary of Rescue Medications during Follow-up Period	ITT
14.1.4.3.3	Summary of Background Therapy	ITT
14.1.5.1.1	Summary of Vaccine and Study Drug Exposure and Compliance	SAF
14.2.1.1.1	Primary Analysis of Proportion of Subjects with a Positive IgG Response to Tetanus Toxoid at Week 16	mITT
14.2.1.1.2	Sensitivity Analysis of Proportion of Subjects with a Positive IgG Response to Tetanus Toxoid at Week 16 – Missing as Non-Responder	ITT
14.2.1.1.3	Sensitivity Analysis of Proportion of Subjects with a Positive IgG Response to Tetanus Toxoid at Week 16 – Observed Case	ITT
14.2.1.1.4	Sensitivity Analysis of Proportion of Subjects with a Positive IgG Response to Tetanus Toxoid at Week 16 – COVID-19 Affected Case	ITT
14.2.2.1.1	Analysis of Proportion of Subjects with a Positive IgG Response to Tetanus Toxoid at Week 16 using Different Criteria	mITT
14.2.2.1.2	Sensitivity Analysis of Proportion of Subjects with a Positive IgG Response to Tetanus Toxoid at Week 16 using Different Criteria – Missing as Non-Responder	ITT
14.2.2.1.3	Sensitivity Analysis of Proportion of Subjects with a Positive IgG Response to Tetanus Toxoid at Week 16 using Different Criteria – Observed Case	ITT
14.2.2.1.4	Sensitivity Analysis of Proportion of Subjects with a Positive IgG Response to Tetanus Toxoid at Week 16 using Different Criteria – COVID-19 Affected Case	ITT

14.2.2.2.1	Analysis of Proportion of Subjects with Serum Anti-tetanus IgG Concentrations of ≥ 0.1 IU/mL at Week 16	mITT
14.2.2.2.2	Sensitivity Analysis of Proportion of Subjects with Serum Anti-tetanus IgG Concentrations of ≥ 0.1 IU/mL at Week 16 – Missing as Non-Responder	ITT
14.2.2.2.3	Sensitivity Analysis of Proportion of Subjects with Serum Anti-tetanus IgG Concentrations of ≥ 0.1 IU/mL at Week 16 – Observed Case	ITT
14.2.2.2.4	Sensitivity Analysis of Proportion of Subjects with Serum Anti-tetanus IgG Concentrations of ≥ 0.1 IU/mL at Week 16 – COVID-19 Affected Case	ITT
14.2.2.3.1	Analysis of Proportion of Subjects with Serum Anti-tetanus IgG Concentrations of ≥ 1.0 IU/mL at Week 16	mITT
14.2.2.3.2	Sensitivity Analysis of Proportion of Subjects with Serum Anti-tetanus IgG Concentrations of ≥ 1.0 IU/mL at Week 16 – Missing as Non-Responder	ITT
14.2.2.3.3	Sensitivity Analysis of Proportion of Subjects with Serum Anti-tetanus IgG Concentrations of ≥ 1.0 IU/mL at Week 16 – Observed Case	ITT
14.2.2.3.4	Sensitivity Analysis of Proportion of Subjects with Serum Anti-tetanus IgG Concentrations of ≥ 1.0 IU/mL at Week 16 – COVID-19 Affected Case	ITT
14.2.2.4.1	Analysis of Proportion of Subjects with Positive Serum Bactericidal Antibody Response to Meningococcal Serogroup C Polysaccharide at Week 16 – Imputed Values	mITT
14.2.2.4.2	Sensitivity Analysis of Proportion of Subjects with Positive Serum Bactericidal Antibody Response to Meningococcal Serogroup C Polysaccharide at Week 16 – Missing as Non-Responder – Imputed Values	ITT
14.2.2.4.3	Sensitivity Analysis of Proportion of Subjects with Positive Serum Bactericidal Antibody Response to Meningococcal Serogroup C Polysaccharide at Week 16 – Observed Case – Imputed Values	ITT
14.2.2.4.4	Sensitivity Analysis of Proportion of Subjects with Positive Serum Bactericidal Antibody Response to Meningococcal Serogroup C Polysaccharide at Week 16 – COVID-19 Affected Case – Imputed Values	ITT
14.2.2.4.7	Analysis of Proportion of Subjects with Positive Serum Bactericidal Antibody Response to Meningococcal Serogroup C Polysaccharide at Week 16 – Non-Imputed Values	mITT
14.2.2.4.8	Sensitivity Analysis of Proportion of Subjects with Positive Serum Bactericidal Antibody Response to Meningococcal Serogroup C Polysaccharide at Week 16 – Missing as Non-Responder – Non-Imputed Values	ITT
14.2.2.4.9	Sensitivity Analysis of Proportion of Subjects with Positive Serum Bactericidal Antibody Response to Meningococcal Serogroup C Polysaccharide at Week 16 – Observed Case – Non-Imputed Values	ITT
14.2.2.4.10	Sensitivity Analysis of Proportion of Subjects with Positive Serum Bactericidal Antibody Response to Meningococcal Serogroup C Polysaccharide at Week 16 – COVID-19 Affected Case – Non-Imputed Values	ITT
14.2.2.5.1	Analysis of Proportion of Subjects with Positive Serum Bactericidal Antibody Response to Meningococcal Serogroup C Polysaccharide using Different Criteria at Week 16 – Non-Imputed Values	mITT
14.2.2.5.2	Sensitivity Analysis of Proportion of Subjects with Positive Serum Bactericidal Antibody Response to Meningococcal Serogroup C Polysaccharide using Different Criteria at Week 16 – Missing as Non-Responder – Non-Imputed Values	ITT
14.2.2.5.3	Sensitivity Analysis of Proportion of Subjects with Positive Serum Bactericidal Antibody Response to Meningococcal Serogroup C	ITT

	Polysaccharide using Different Criteria at Week 16 – Observed Case – Non- Imputed Values	
14.2.2.5.4	Sensitivity Analysis of Proportion of Subjects with Positive Serum Bactericidal Antibody Response to Meningococcal Serogroup C Polysaccharide using Different Criteria at Week 16 – COVID-19 Affected Case – Non-Imputed Values	ITT
14.2.2.6.1	Analysis of Proportion of Subjects with Positive Serum Bactericidal Antibody Response to Meningococcal Serogroup C Polysaccharide using Different Criteria at Week 16 – Imputed Values	mITT
14.2.2.6.2	Sensitivity Analysis of Proportion of Subjects with Positive Serum Bactericidal Antibody Response to Meningococcal Serogroup C Polysaccharide using Different Criteria at Week 16 – Missing as Non-Responder – Imputed Values	ITT
14.2.2.6.3	Sensitivity Analysis of Proportion of Subjects with Positive Serum Bactericidal Antibody Response to Meningococcal Serogroup C Polysaccharide using Different Criteria at Week 16 – Observed Case – Imputed Values	ITT
14.2.2.6.4	Sensitivity Analysis of Proportion of Subjects with Positive Serum Bactericidal Antibody Response to Meningococcal Serogroup C Polysaccharide using Different Criteria at Week 16 – COVID-19 Affected Case – Imputed Values	ITT
14.2.2.7.1	Analysis of Geometric Mean Concentration of Anti-tetanus IgG at Baseline and Week 16	mITT
14.2.2.7.2	Sensitivity Analysis of Geometric Mean Concentration of Anti-tetanus IgG at Baseline and Week 16 – Observed Case	ITT
14.2.2.7.3	Sensitivity Analysis of Geometric Mean Concentration of Anti-tetanus IgG at Baseline and Week 16 – COVID-19 Affected Case	ITT
14.2.2.8.1	Analysis of Geometric Mean Titers of MenC SBA at Baseline and Week 16 – Imputed Values	mITT
14.2.2.8.2	Sensitivity Analysis of Geometric Mean Titers of MenC SBA at Baseline and Week 16 – Observed Case – Imputed Values	ITT
14.2.2.8.3	Sensitivity Analysis of Geometric Mean Titers of MenC SBA at Baseline and Week 16 – COVID-19 Affected Case – Imputed Values	ITT

CCI		
14.3.1.1	Overall Summary of Treatment-Emergent Adverse Events	SAF
14.3.1.2	Treatment-Emergent Adverse Events by System Organ Class and Preferred	SAF
	Term	

14.3.1.3	Treatment-Emergent Adverse Events Related to Study Drug by System Organ Class and Preferred Term	SAF
14.3.1.4	Serious Treatment-Emergent Adverse Events by System Organ Class and Preferred Term	SAF
14.3.1.5	Serious Treatment-Emergent Adverse Events Related to Study Drug by System Organ Class and Preferred Term	SAF
14.3.1.6	Treatment-Emergent Adverse Events by System Organ Class, Preferred Term and Maximum Severity	SAF
14.3.1.7	Treatment-Emergent Adverse Events Related to Study Drug by System Organ Class, Preferred Term and Maximum Severity	SAF
14.3.1.8	Treatment-Emergent Adverse Events Leading to Study Drug Withdrawal by System Organ Class and Preferred Term	SAF
14.3.1.9	Treatment-Emergent Adverse Events of Special Interest by System Organ Class and Preferred Term	SAF
14.3.1.10	Treatment-Emergent Adverse Events Leading to Temporary Interruption of Study Drug by System Organ Class and Preferred Term	SAF
14.3.1.11	Treatment-Emergent Adverse Events Leading to Study Discontinuation by System Organ Class and Preferred Term	SAF
14.3.1.12	Most Common Treatment-Emergent Adverse Events (Frequency > 5%) by Preferred Term	SAF
14.3.1.13	Adjudicated Treatment Emergent Adverse Events (TEAEs) by SOC and PT	SAF
14.3.1.14	Treatment Emergent Adverse Events (TEAEs) of Asthma and Asthma related events reported by Investigator with Adjudication Outcome by IAC	SAF
14.3.1.15	Confirmed Adjudicated Treatment Emergent Adverse Events (TEAEs) by SOC, PT and Maximum Severity	SAF
14.3.2.1	Listing of Serious Adverse Events	SAF
14.3.2.2	Listing of Adverse Events Leading to Study Drug Withdrawal	SAF
14.3.2.3	Listing of Adverse Events of Special Interest	SAF
14.3.2.4	Listing of Adjudicated Asthma Treatment-Emergent Adverse Events (TEAEs)	SAF
14.3.2.5	Listing of Adjudicated Asthma Treatment-Emergent Adverse Events (TEAEs) Comments	SAF
14.3.4.1.1.1	Summary of Observed Values and Changes from Baseline for Hematology Value by Visit	SAF
14.3.4.1.1.2	Shift from Baseline of Hematology Values by Visit and by Reference Range	SAF
14.3.4.1.1.3	Proportions of Subjects with Potentially Clinically Significant Hematology Value	SAF
14.3.4.1.1.4	Listing of Subjects with Potentially Clinically Significant Hematology Value	SAF
14.3.4.1.2.1	Summary of Observed Values and Changes from Baseline for Chemistry Value by Visit	SAF
14.3.4.1.2.2	Shift from Baseline of Chemistry Values by Visit and by Reference Range	SAF
14.3.4.1.2.3	Proportions of Subjects with Potentially Clinically Significant Chemistry Value	SAF
14.3.4.1.2.4	Listing of Subjects with Potentially Clinically Significant Chemistry Value	SAF
14.3.4.1.3.1	Summary of Observed Values and Changes from Baseline for Urinalysis Value by Visit	SAF
14.3.4.1.3.2	Shift from Baseline of Urinalysis Values by Visit and by Reference Range	SAF
14.3.4.1.3.3	Proportions of Subjects with Potentially Clinically Significant Urinalysis Value	SAF
14.3.4.1.3.4	Listing of Subjects with Potentially Clinically Significant Urinalysis Value	SAF

14.3.4.2.1	Summary of Observed Values and Changes from Baseline for Vital Signs, Height and Weight by Visit	SAF
14.3.4.2.2	Shift from Baseline of Vital Signs, Height and Weight by Visit and by Reference Range	SAF
14.3.4.2.3	Proportions of Subjects with Potentially Clinically Significant Vital Signs, Height and Weight	SAF
14.3.4.2.4	Listing of Subjects with Potentially Clinically Significant Vital Signs, Height and Weight	SAF
14.3.4.3	Summary of 12-Lead Electrocardiogram (ECG) Overall Interpretation	SAF
14.3.4.4	Summary of Physical Examination	SAF
14.3.4.5.1	Summary of Asthma Control Test (ACT)	SAF
14.3.4.5.2	Summary of Asthma Control Test (ACT) Score <= 19	SAF
14.3.4.6	Summary of Respiratory Examination	SAF
14.3.4.7.1	Summary of Peak Expiratory Flow (PEF)	SAF
14.3.4.7.2	Summary of Peak Expiratory Flow (PEF) < 80% of Predicted Value	SAF

